11.2. Sample Size

No formal statistical hypothesis is to be tested for this post approval study. The planned sample size is empirical.

11.3. Analysis Sets

11.3.1. Intent-to-Treat Set

The intent-to-treat set will include all procedures/patients with an attempted TIP procedure using a study device regardless it is successful, or an alternative device is needed.

This set will be the base for assessment of technical success rate and overall procedure success rate, as well as overall device safety.

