6.6. Target Enrollment

Approximately 60 subjects (30 per group) indicated to undergo a TIPS procedure who are eligible for the study and agree to participation will be enrolled. Subjects will be enrolled in the study once and have one TIPS procedure.

Each investigational site will be limited to enroll up to 16 subjects.

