7.5. Informed Consent

Subjects must be fully counseled and informed of their study options, risks, and benefits, and have every opportunity to ask questions about participation in this study. The subject will sign the IRB-approved ICF prior to initiation of the TIPS procedure. For subjects who are unable to provide written consent, consent may be obtained from the subject's legally authorized representative (LAR) per the institution/IRB policies, if allowed.

A copy of the signed statement of informed consent will be provided to the subject and/or LAR.

The PI or qualified designee is responsible for obtaining written informed consent from each subject prior to participation in the clinical study. Should the Investigator delegate the responsibility of conducting the informed consent process to a designee, the Investigator must ensure and document appropriate training of the authorized designee.

If new information regarding the investigational device becomes available and/or changes to the protocol affect a subject's future health and medical care, subjects will be provided with the information and may be asked to sign a revised informed consent form.

The consent process must be documented in the subject's medical record. The original, fully signed consent form will be kept in the site's study file or subject medical record per the institution policy. A fully signed copy must also be provided to the subject and/or LAR.

Subjects that decline participation in the study, do not provide consent, or withdraw consent prior to initiation of the TIPS procedure will be documented as a screen failure on the study screening and enrollment log.

Once the study-specific informed consent form (ICF) is signed, the subject is considered enrolled.

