7.7. Randomization

Randomization will occur after an eligible subject has signed the ICF and prior to initiation of the TIPS procedure. Subjects will be randomly assigned at a 1:1 ratio into one of the two study groups (Scorpion or Cook) via a centralized randomization service.

Once the randomization assignment is received, the physician will determine the model he/she wants to use based on preference, training, and the subject case before beginning the procedure.

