11.3.3. Safety Population

Safety set will include all procedures/patients defined in the intent-to-treat set.

This set will be the base for the overall study safety assessment.

For study device-specific post-operation safety assessment, only those included in the primary effectiveness set will be used.

Comparability analyses between the two study groups will be conducted on the Intent-to-Treat analysis set.

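### The intent-to-treat set starts at an attempted procedure, not at randomisation, and pre-procedure withdrawals are logged as screen failures, so randomised subjects can drop out of the analysis with no count by arm.

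*Combined protocol and SAP*

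**What the plan says.** The order of events is consent, randomisation, procedure. Section 7.5 fixes enrolment at consent: "Once the study-specific informed consent form (ICF) is signed, the subject is considered enrolled". Section 7.7 then states: "Randomization will occur after an eligible subject has signed the ICF and prior to initiation of the TIPS procedure". Section 7.8 makes the study open-label, and Section 7.7 has the physician receive the assignment and choose a model before starting.

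Section 11.3.1 defines the intent-to-treat set as "all procedures/patients with an attempted TIP procedure using a study device", and keeps attempts that fail or that end with a different device. On its use, the section says: "This set will be the base for assessment of technical success rate and overall procedure success rate, as well as overall device safety". Section 11.3.3 adds: "Safety set will include all procedures/patients defined in the intent-to-treat set". It also places the baseline comparability analysis on the intent-to-treat set.

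Section 7.5 says that subjects who "withdraw consent prior to initiation of the TIPS procedure will be documented as a screen failure". It makes no exception for subjects who have been randomised. Section 8.8 also allows withdrawal at the discretion of the Principal Investigator or the sponsor, and gives no rule for a withdrawal between randomisation and procedure.

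**The concern.** An intent-to-treat set should be fixed at randomisation, so that nothing that happens once the assignment is known can affect who is analysed. Here entry depends on a later event, the attempt. Physicians know the assignment by then and have discretion to withdraw subjects. If the subjects who do not proceed differ between arms in number or prognosis, the two analysed groups are no longer the two randomised groups.

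The set carries the procedural success rate, which is the primary effectiveness endpoint, and the overall safety rates. The comparability analysis uses the same subjects, so it could not show who had been lost. Sections 3 and 3.3 say the results will support an initial CE mark application, and a rate presented there as intent-to-treat should be one.

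**Working it through.** **Following a randomised subject who has no attempted procedure**

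1. Consent is signed, so the subject is enrolled (7.5).
2. The assignment is issued and is known to the physician (7.7, 7.8).
3. The procedure does not start. If the subject withdrew consent, Section 7.5 logs a screen failure. If the procedure was cancelled, or the investigator or sponsor withdrew the subject, Section 7.5 does not apply.
4. In every case the subject fails the entry condition of 11.3.1, and so is also outside the safety set and the comparability analysis (11.3.3).
5. No section brings the subject back or asks for a count by arm. Section 10.5.1 keeps adverse events between consent and procedure off the eCRF, so little trace remains there.

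Section 7.5 is also inconsistent with itself: the same person is enrolled and a screen failure.

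**Size**

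The plan has no figure to reproduce beyond 2 x 30 = 60. Section 11.2 calls the sample size empirical, and no non-start rate is given. Everything below is assumed except the 30 per group.

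Plausible losses: if 2%, 5% or 10% of 60 randomised subjects are not attempted, the expected numbers are 60 x 0.02 = 1.2, 60 x 0.05 = 3 and 60 x 0.10 = 6, over both arms.

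Effect on the rate: let 30 be randomised per arm and s succeed in each, so the true difference is zero. Let k subjects who would have failed leave one arm before the procedure.

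- Set as written: s / (30 - k) in that arm, s / 30 in the other.
- All randomised, non-starters counted as not successful: s / 30 in both arms, for any k.

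| s | k | Set as written | Other arm | False gap (points) |
|---|---|---|---|---|
| 27 | 1 | 27/29 = 93.1% | 90.0% | 3.1 |
| 27 | 2 | 27/28 = 96.4% | 90.0% | 6.4 |
| 27 | 3 | 27/27 = 100% | 90.0% | 10.0 |
| 24 | 1 | 24/29 = 82.8% | 80.0% | 2.8 |
| 24 | 2 | 24/28 = 85.7% | 80.0% | 5.7 |
| 24 | 3 | 24/27 = 88.9% | 80.0% | 8.9 |

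The largest gap, 27/27 against 27/30, gives p = 0.09 by Pearson's chi-square without continuity correction. These cases assume that all losses fall in one arm and are all would-be failures, so they show what a few subjects can do rather than what to expect.

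The scoring rule can also err the other way. If two would-be successes out of 27 do not start, the set as written gives 25/28 = 89.3% and the all-randomised analysis gives 25/30 = 83.3%, against a true 90.0%. This is why both analyses should be shown.

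**The case against.** The best case for the plan is that the gap is narrow and the stakes are limited. Table 6 puts randomisation in the Day 0 column, cases are scheduled and non-emergent (7.4), and investigators must be willing to use either set (4.3). The 11.3.1 set keeps failed procedures and switches to an alternative device, which are the commoner routes by which failures go missing. Withdrawals leave some record: subject IDs are not reused (7.6), withdrawals are documented (8.8) and the information is retained (13.4). No formal hypothesis is tested (11.1). All of this stands, and it makes the likely number small. It does not close the gap: Section 7.7 and the Table 6 footnote require only that randomisation precede the procedure, and no record is required by arm.

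A reader might infer three stronger points that the documents do not support.

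- **Subjects may be analysed by the device used.** Section 11.3.1 alone does not name the arm of analysis. But Section 6.4.1 makes failure with the randomised assignment a treatment failure, and Section 7.7 defines the groups by random assignment. Naming the assigned arm is a clarification.
- **The sample size falls short.** Section 6.6 plans "Approximately 60 subjects (30 per group) indicated to undergo a TIPS procedure", and Section 11.2 sets no power or precision target. Fewer treated subjects would breach no stated figure.
- **Selection by arm will occur.** The documents show only that it is possible. Section 7.7 has the physician receive the assignment and does not describe telling the subject.

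It is also fair to object that enlarging the set changes nothing by itself. Section 11.4 does not impute missing data, so a subject with no attempt could still drop out of the denominator. The scoring rule must therefore be written down.

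**Conclusion.** The concern holds in a limited form. The set named intent-to-treat is a treated set, and Section 7.5 gives a randomised subject who withdraws consent before the procedure a status that conflicts with being enrolled. Randomised subjects can leave the main analyses after an open assignment, without being accounted for by arm.

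The size cannot be derived from the documents. Under the stated assumptions, one to three lost would-be failures in an arm of 30 raise its success rate by 2.8 to 10.0 points when the arms are truly equal. Because the window is probably short, the expected number is low and may be zero. This is a correction of wording and reporting that should be made, because the affected rates are the study's main descriptive results. It does not show that the comparison will be biased.

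**What to change.** - **Section 11.3.1:** define the intent-to-treat set as all randomised subjects, analysed in their assigned arm. State that a randomised subject with no attempted procedure counts as not achieving procedural success in that analysis.
- **Sections 11.3.1 and 11.3.3:** rename the current set treated (modified intent-to-treat). Keep it for safety, where exposure to a procedure is the natural condition, and as a supportive effectiveness analysis. Run the comparability analysis on all randomised subjects.
- **Section 7.5:** limit screen failure to subjects not yet randomised. Record later withdrawals as post-randomisation withdrawals.
- **Reporting:** tabulate subjects randomised but not attempted by arm, with reason, including cancelled procedures and withdrawals directed by the investigator or sponsor.

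The cost is wording and one table, with no new assessment or visit. The reported success rate may be slightly lower, and the scoring rule will understate success when a non-starter would have succeeded. Presenting the treated-set rate alongside lets the reader see both.

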11.3.2. Primary Effectiveness Set

The primary effectiveness set will include procedures/patients who have a successful procedure with only a study device (i.e., no need of an alternative device).

This set will be the base for assessment of cannulation time, fluoroscopy time, procedure duration, as well as other device-specific outcomes.

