3.2. Prior Investigations

The Rosch-Uchida and Colapinto sets manufactured by Cook Medical (Bloomington, Indiana, US) are two different needle sets currently available and most encountered. A recent systematic review of literature showed that the overall incidence of PVPC with the Cook sets was 3.6%.⁶ The procedure duration varies in literature due to protocol differences and imaging techniques used. David et al.⁷ reported a mean procedure duration of 86.2 minutes using ultrasound guidance. In a study evaluating time to portal vein access, mean time to portal venous access was statistically significant between conventional fluoroscopy at 46 minutes and intravascular US-guided TIPS at 31 minutes.⁸

In the paucity of studies available which focus on portal vein access in TIPS interventions, there are few that demonstrate significant differences between the number of needle passes. The data is incomplete because fewer than half of conventional TIPS cases in literature included a recording of the actual number of passes. The Scorpion devices allow for bi-directional positioning of the needle or stylet for precise placement during portal vein puncture.

In a retrospective study of 15 cases with Scorpion X (Needle model), technical success was achieved in 100% of cases with an average of 2.7 passes, and because of the bi-directional needle, no cases required adjustment to the curvature of the needle.⁹

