6.4. Study Endpoints

6.4.1. Primary Effectiveness Endpoint

The primary effectiveness endpoint is procedural success defined as creation of the parenchymal tract between the hepatic vein and an intrahepatic branch of the portal vein and confirmed by portogram (CO₂/contrast).

Failure to create the parenchymal tract between the hepatic vein and the portal vein with the randomized assignment will be considered a treatment failure. A minimum of 5 needle passes should be attempted before selecting the alternative set.

In the event of a treatment failure, the physician will follow their standard of care procedures and/or use another commercially available product. The patient should be followed in the study through hospital discharge for adverse event monitoring.

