6.4.3. Secondary and Exploratory Endpoints

The secondary and exploratory endpoints of this clinical study are outlined in **Table 5**.

TABLE 5. OVERVIEW OF SECONDARY AND EXPLORATORY ENDPOINTS

Endpoint	Description / Definition
Secondary Endpoints	
Portal Vein Access (PVA) time	Time (in minutes) from initial needle throw to portal vein access as confirmed by portogram
Technical success	Creation of a shunt (stent bridging) between the portal and systemic veins
Number of needle passes	Count of needle throws between the hepatic and portal vein to create the parenchymal tract
Procedure duration	Interval (in minutes) from first jugular access for TIPS creation to removal of catheters from subject
Fluoroscopy time	Measured in minutes
Device-related complications	Incidence of complications related to the device as judged by the Principal Investigator
Exploratory Endpoints	

Change in MELD score	Change in score from Screening to Day 30
Change in Child-Pugh score	
Radiation dosage	Measured in air kerma (mGy)
Contrast volume used	Measured in mL
Length of Hospital Stay	Measured in days
Number of ICU days	Measured in days
Change in HPVG	Measured in mm Hg

MELD = Model for End-Stage Liver Disease; ICU = Intensive Care Unit; HPVG = Hepatic Venous Pressure

Gradient

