8.3. TIPS Procedure (Day 0)

The TIPS procedure will be completed in a clinical setting with adequate angiographic equipment and institutional facilities, physiologic monitoring equipment, and support personnel.

Transjugular liver access will be obtained using either the Scorpion set or Cook set per randomization assignment and physician choice of model. The procedure will be performed in accordance with the Scorpion IFU or the Cook IFU. Refer to the current IFU included with the device for techniques and methods for pre-procedure preparation and directions for use. The specific model and treatment details (e.g., access site, access side, stent, etc.) will be determined by the physician based on the condition of the subject.

A minimum of 5 needle passes should be attempted with the initial device assigned through randomization before selecting the alternative manufacturer set. If an alternative manufacturer set is selected, the information will be recorded as part of the study records.

The following procedure data are to be collected and recorded in the subject's medical record or other applicable source documents which will be reported on the appropriate eCRF:

Jugular access site
Number of needle passes
Hepatic vein used for access
Access device used
Portal vein access site
Imaging used
Alternate access sites/techniques used
Sheath used
Stent used, dilated to what size
Pressure gradient measurements: pre- and post-delivery of stent
Presence of residual varices
Adverse events (during and post procedure)
Record Concomitant Medications (only rifaximin, lactulose, and medications which are an anticoagulant, antiplatelet, or diuretic will be recorded)

A portogram must be obtained to confirm creation of the parenchymal tract between the hepatic vein and an intrahepatic branch of the portal vein upon portal vein access and following stent deployment.

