11. STATISTICAL CONSIDERATIONS

11.1. Statistical Design and Methodology

For this post approval study, no formal study hypothesis will be tested. Study outcomes will be presented using descriptive statistics for each treatment group. In addition, outcomes by demographic and clinical characteristics will be presented. For exploratory purposes, between-group differences in study endpoints will be assessed with comparative tests. Statistical analyses will be performed using SAS (SAS Institute, Cary, NC, USA).

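### Access time, fluoroscopy time and procedure duration are compared only among procedures that succeeded with the assigned set, so randomisation no longer protects these comparisons and differences can be understated or created

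*Combined protocol and SAP*

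**What the plan says.** The Primary Effectiveness Set in section 11.3.2 "will include procedures/patients who have a successful procedure with only a study device", with no alternative device needed. Its use is stated directly: "This set will be the base for assessment of cannulation time, fluoroscopy time, procedure duration, as well as other device-specific outcomes". Cannulation time is not defined under that name; I read it as the portal vein access (PVA) time of Table 5. Needle passes are not named but can be read into the last phrase.

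Section 6.4.1 defines failure on the primary endpoint by the same event: "Failure to create the parenchymal tract between the hepatic vein and the portal vein with the randomized assignment will be considered a treatment failure". Section 8.3 adds: "A minimum of 5 needle passes should be attempted with the initial device assigned through randomization before selecting the alternative manufacturer set". No maximum is given.

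Section 11.3.1 defines a set of all attempted procedures, whether or not they succeeded, but gives it other work: "This set will be the base for assessment of technical success rate and overall procedure success rate, as well as overall device safety". Section 11.1 plans the between-group tests: "For exploratory purposes, between-group differences in study endpoints will be assessed with comparative tests". Section 11.1.2 names the t-test for continuous variables. Section 11.3.3 places the comparability analysis of the two groups on the Intent-to-Treat set.

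**The concern.** Membership of the set is decided after randomisation, by the outcome the device is meant to influence. The patients left in each arm need not be alike, even if the randomised groups were. Baseline comparability is planned on the Intent-to-Treat set, so imbalance created by the selection would not show there. Adjusting for baseline variables, as section 11.1.2 allows, cannot bring back the excluded failures.

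The exclusions are probably not a random sample. A switch should normally follow at least 5 passes, whereas the one earlier Scorpion X series in section 3.2 averaged 2.7 passes (15 retrospective cases). The cases removed are therefore likely to be long ones. The study is also open-label with no upper limit on passes, so the readiness to switch can differ between arms.

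Shorter procedure and fluoroscopy times and fewer passes are among the potential benefits listed in section 5.1, and sections 3 and 3.3 say the data will support an initial CE mark application. These are comparisons that readers will look at.

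**Working it through.** The plan states no figure to reproduce: the sample size is called empirical and no effect size, SD or failure rate is given. I therefore checked whether the text has the effect described, and then sized it under stated assumptions.

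**Text.** PVA time ends at confirmed access, so in a failed case it is unfinished when the set is given up, not absent. Procedure duration in Table 5 runs "from first jugular access for TIPS creation to removal of catheters from subject", which can be observed in every procedure, including those that needed a second set. I found no all-attempted or sensitivity analysis of the time endpoints in section 11, and no rule for PVA time after failure. Section 11.4 (no imputation) does not deal with exclusion by design.

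**Illustration 1: needle passes.** Assume a constant success probability p per pass, with the set given up after K passes.
- Passes spent with the assigned set: E[min(N,K)] = (1 − (1−p)^K)/p
- Success-only mean: Σ_{k≤K} k·p(1−p)^(k−1) / (1 − (1−p)^K)
- Share lost: 1 − (success-only difference)/(difference in passes spent)

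For p = 0.2 vs 0.4:

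| K | Success | Success-only means | Diff. | Passes spent | Diff. | Lost |
|---|---|---|---|---|---|---|
| 5 | 67% / 92% | 2.56 / 2.08 | 0.48 | 3.36 / 2.31 | 1.06 | 54% |
| 7 | 79% / 97% | 3.14 / 2.30 | 0.84 | 3.95 / 2.43 | 1.52 | 45% |
| 10 | 89% / 99% | 3.80 / 2.44 | 1.36 | 4.46 / 2.48 | 1.98 | 31% |
| 15 | 97% / 100% | 4.45 / 2.49 | 1.96 | 4.82 / 2.50 | 2.33 | 16% |

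For p = 0.5 vs 0.6 and K = 5 (97% vs 99% success), the success-only difference is 0.22 against 0.29 passes spent: 22% lost, or about 0.07 of a pass. At K = 10 the loss is 2%. With one K for both arms, this model can only show attenuation.

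**Illustration 2: PVA time with identical sets.** The mean m = 46 min comes from section 3.2 ("mean time to portal venous access was statistically significant between conventional fluoroscopy at 46 minutes"). The lognormal shape and CV 0.6 are assumptions. One set never fails; the other fails in a fraction f, and failure has correlation ρ with case length on the underlying normal scale.
- s = √ln(1 + CV²) = √ln 1.36 = 0.555; c = Φ⁻¹(1 − f) = 1.282 for f = 0.10
- Success-only mean = m·Φ(c − ρs)/(1 − f)

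| f | ρ | Success-only mean (min) | False advantage (min) |
|---|---|---|---|
| 3/30 | 0 | 46.0 | 0 |
| 3/30 | 0.5 | 43.1 | 2.9 |
| 3/30 | 0.8 | 40.8 | 5.2 |
| 3/30 | 1 | 39.2 | 6.8 |
| 1/30 | 1 | 42.8 | 3.2 |

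At ρ = 1 and f = 0.10, CV 0.4 gives 41.7 min (4.3 min advantage) and CV 0.8 gives 36.7 min (9.3 min).

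**Independent check by simulation.** Inputs: set A per-pass success 1/2.7 (from the 2.7 mean passes), set B 0.30 down to 0.15, 5 min per pass with lognormal noise, a switch after 5, 8 or 10 failed passes, with and without patient-level difficulty. All but the 2.7 are assumed. Where the sets truly differed, the success-only comparison kept about 20% to 72% of the all-attempted difference in minutes. With identical sets, but one arm switching after 10 passes and the other after 5, the all-attempted difference was 0.0 to 0.1 min, while the success-only comparison showed the early-switching arm 2.3 to 3.1 min faster.

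**Loss of numbers is secondary.** At an assumed two-sided 5% level and 80% power, the detectable difference is 2.80·√(1/30 + 1/30) = 0.72 SD with 30 per arm and 2.80·√(1/30 + 1/27) = 0.74 SD with 30 vs 27.

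**The case against.** The best defence is that the plan asks a device-specific question. PVA time has no completed value in a failed case, and total times after a switch include work done with another set. Nor are failures hidden: they count against the set on the primary endpoint, and success rates use all attempted procedures, so a set that only looks fast would show a lower success rate beside it. The endpoints are secondary, the tests exploratory, and precision is poor. With CV 0.6 the SD is 0.6 × 46 = 27.6 min, and the 95% half-width with 30 vs 27 cases is 1.96 × 27.6 × √(1/30 + 1/27), about 14 min, roughly twice the extreme 6.8 min artefact. The 54% figure needs 67% vs 92% success and a switch exactly at the stated minimum, while the earlier Scorpion X series reports technical success in all 15 cases.

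Much of this stands, and it limits the weight of the point. If both arms nearly always succeed, the distortion is small. Illustration 1 also measures passes spent, not the endpoint recommended below, so its percentages do not say how much the fix would recover. Worst ranks do count failure a second time and give up a mean difference in minutes. But exploratory status removes the claim about error rates, not the bias, and a wide interval does not make a selected comparison a randomised one. The device-specific question justifies keeping the success-only summary, not making it the only analysis.

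**Conclusion.** The concern holds. As written, the plan compares the time endpoints in groups selected by the primary outcome, and nothing else in section 11 repairs this. Understatement of a real difference is the likely direction when the slower set also fails more often. A false difference between equal sets is possible when failures are concentrated in long cases in one arm, or when the arms differ in how soon they switch.

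The size cannot be fixed from the documents, because failure rates and switching behaviour are not given. It ranges from negligible when success is nearly universal to several minutes of PVA time with 3 failures in 30. Procedural success is analysed on all attempted procedures and is unaffected. I rate this as something that should be fixed, with high confidence in the reading of the text and only illustrative confidence in the magnitudes.

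**What to change.** Make the section 11.3.1 set the primary base for these endpoints, and state that patients are analysed by assigned set; the section does not currently say so.

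- **Fluoroscopy time and procedure duration:** report observed totals with failures included, described as the result of starting with the assigned set rather than of the device alone. Give procedures abandoned without a shunt the worst rank, so that an early stop does not count as a fast procedure.
- **PVA time and needle passes:** analyse time or passes to access with the assigned set, counting failures as never achieving access (cumulative incidence or worst rank). Where worst ranks are used, for any of these endpoints, replace the t-test of section 11.1.2 with a rank test and report medians.
- **Data:** record elapsed time and pass count when the assigned set is given up. Confirm that fluoroscopy time and procedure start and stop times are captured in every case; the list in section 8.3 names neither fluoroscopy time nor procedure duration, though the case report forms may cover them.
- **Success-only summary:** keep it as a labelled supplementary description, with exclusions by arm and baseline characteristics for that subset.

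The cost is plan wording, rank-based code and one added data item. Reported times may look longer, and totals after a switch no longer isolate the device, which is why the success-only summary stays alongside. No clinical procedure changes.
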